5.2 Screening Process

The study coordinator will screen the endoscopy schedule daily to look for potentially eligible patients. The study coordinator will inform the gastroenterologist of potentially eligible patients.

6. PROTOCOL PROCEDURES, METHODS, AND DURATION (LAYMAN'S DESCRIPTION)

After confirmation of patient eligibility, the study coordinator will obtain written informed consent. The informed consent process may take up to 45 minutes. The study coordinator will review the labs, order any missing research study labs to calculate the FIB-4 index and MELD score, and schedule the DECT exam at a time that is convenient for the patient but within 2 weeks of the endoscopy. Women of childbearing potential will receive either a blood draw or urine pregnancy test to make sure they are not pregnant. Baseline clinical and laboratory data will be gathered by the study coordinator and entered into a REDCap database.

The patient will undergo the upper gastrointestinal (GI) endoscopy procedure and recovery per standard of care. The endoscopy results (e.g. grade of esophageal varices) will be entered into the REDCap database. After the post-endoscopy procedure recovery period and prior to discharge, the study coordinator will complete a questionnaire with the patient to capture the patient's experience and document any complications related to the upper GI endoscopy. The questionnaire will take 15 minutes to complete. The questionnaire data will be entered into the REDCap database. The patient will be provided with the date and time of the scheduled DECT study, which may be on the same day as the endoscopy or within 2 weeks from endoscopy. The patients will be scheduled for DECT at Leeds or Gardendale, as both Imaging Centers have a *Dual Energy GE Revolution CT with GSI Xtream*, which is needed for this study. The patient will be discharged per standard of care, and the questionnaire data will be entered into the REDCap database by the study coordinator.

One the day of the DECT imaging, the patient will have nothing by mouth to eat or drink for 4 hours prior to the DECT exam. The patient will check in at the imaging center for their scheduled DECT exam. An intravenous line will be placed by the technologist, and the patient will undergo DECT imaging with intravenous iodinated contrast. CT imaging will be obtained in the late arterial phase using bolus tracking and in the portal venous phase using a dual energy CT approach. In order to reduce radiation dose, the noncontrast and delayed phases (present in a routine 4-phase liver CT) will not be obtained. The time from check in to completion of the imaging study is expected to be 45 minutes. After imaging, the study coordinator will complete a questionnaire with the patient to capture the patient's experience and document any complications related to the CT imaging procedure. The questionnaire will take 15 minutes to complete. The patient will be given a \$75 gift card incentive for their time, and the patient will be discharged. The questionnaire data will be entered into the REDCap database.

The patients will be contacted by phone by the study coordinator at 1- and 2-years post endoscopy to capture information on complications of cirrhosis, particularly bleeding episodes and treatment of high-risk gastroesophageal varices. The phone interview is expected to take 15 minutes to complete. If the patient has a visit to the hepatologist, the interview may alternatively be conducted at that time per patient preference. The electronic medical records will also be searched for complication of cirrhosis and bleeding episodes. The study coordinator will conduct the interviews and record all data in a REDCap database. The patients will be discharged from the study after the 2 year follow up interview.

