2. BACKGROUND AND RATIONALE

Cirrhosis leads to portal hypertension and development of gastroesophageal varices, which are the most common cause for bleeding in cirrhosis and a major cause of death. Bleeding varices have a 6-week mortality of 15%-25%.^{1,2} About 50% of patients with cirrhosis have varices, and 30% have large varices (>5 mm) that are high risk for bleeding.³

The American Association for the Study of Liver Disease (AASLD) recommends screening endoscopy every 2 years to evaluate for varices, and annual surveillance for those with small varices on endoscopy.⁴ Patients at a high risk of bleeding with large varices, small varices and red wale signs (an endoscopic finding), or small varices and decompensated cirrhosis proceed to treatment such as prophylactic band ligation and beta blockers.^{5,6,7} Conversely, patients with no varices or small varices (≤ 5 mm) continue surveillance efforts by endoscopy to monitor for development of large varices.^{3,7,8} Unfortunately, endoscopy is costly, requires sedation, is poorly tolerated, is subject to high inter-observer

variability, cannot detect other signs or portal hypertension or para-esophageal varices that are at risk for future bleeding events, and is associated with risks that include bleeding, esophageal injury and aspiration.⁹ Many of these factors contribute to poor patient compliance with AASLD recommendations.

Noninvasive methods for detecting, grading, and risk stratification of esophageal varices are needed. Imaging tests such as ultrasound elastography to measure liver stiffness have been proposed as a method to predict the presence of varices but have insufficient accuracy to eliminate the need for endoscopy.¹⁰ An ideal biomarker to screen for esophageal varices would be part of the routine standard of care of patients with cirrhosis, noninvasive, rapid, less expense than endoscopy, highly accurate, highly reproducible, and would require no sedation, provide a quantitative measure of the size of the varices, provide a mechanisms to assess the risk of future bleeding, allow for an assessment for other signs of portal hypertension, and provide other benefits to the patient (e.g. detect ascites and HCC and assess liver vasculature).

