4.2 Exclusion Criteria

- 4.2.1** Inability to provide written informed consent
- 4.2.2** History of bleeding gastroesophageal varices, variceal intervention or portosystemic shunt
- 4.2.3** Prior liver transplant
- 4.2.4** History of malignancy
- 4.2.5** Severe chronic kidney disease with estimated glomerular filtration rate (GFR) < 30 mL/min/1.73 m²
- 4.2.6** Presence of acute kidney injury
- 4.2.7** Prior iodinated contrast allergy
- 4.2.8** Patient weight >300 lbs
- 4.2.9** Multiphasic liver CT within 3 months of upper endoscopy
- 4.2.10** Pregnancy

4.3 Inclusion of all races and ethnic groups are eligible for this trial. There is no bias towards age or race in this trial. The trial is open the accrual of women and men.

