5. RECRUITMENT AND SCREENING

5.1 Recruitment Process

Patients presenting to the Highlands Gastroenterology Endoscopy Center or to the Kirklin Clinic Gastroenterology Endoscopy Center will initially be approached by the hepatologist ([name], sub-investigator who routinely performs surveillance endoscopy procedures) to ask if the patient would be interested in the study. If the patient is interested, the study coordinator will meet with the patient prior to endoscopy, answer questions, review the inclusion/exclusion criteria, and obtain informed consent. The study coordinator will review the labs, order any missing research study labs, and schedule the DECT exam. The patients will be directed to our outpatient facilities at Leeds or

Gardendale, as both centers have a *Dual Energy GE Revolution CT with GSI Xtream* (DECT). After imaging, the patient will be given a \$75 incentive for their time, and the patient will be discharged. Patients will provide consent for a follow up interview to evaluate for liver-related events, particularly bleeding varices. The study coordinator will arrange the interview and record all data in a secure web-based REDCap research database.

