11. DATA AND IMAGE ANALYSIS

11.1 Clinical Evaluation:

Baseline clinical and laboratory data (**Table 1**) will be gathered by the study coordinator and entered into a password-restricted and secure web-based REDCap database. Data from the post-endoscopy and post-DECT questionnaires will be entered into the REDCap database.

11.2 Endoscopy Evaluation:

All patients will undergo standard of care upper gastrointestinal endoscopy in The Kirklin Clinic or Highlands Hospital endoscopy suites for surveillance of gastroesophageal varices. The endoscopists will report the grade of esophageal varices: grade 0 = none, grade 1 = small (≤ 5 mm), and grade 2 = large (> 5 mm). The endoscopists will also record the presence or absence of a red wale or red spot sign, presence or absence of gastric varices, presence or absence of signs of portal gastropathy, presence or absence of gastritis, duodenitis, or a gastric or duodenal ulcer, and presence or absence of active bleeding (and location if present). The hepatologist will also be contacted to confirm the substage of cirrhosis, which includes the information from the surveillance endoscopy.

11.3 Image Evaluation:

11.3.1 DECT Image Acquisition:

Table 2. Relevant Clinical and Laboratory Data

- **Demographics:** age, gender, race, ethnicity, body mass index
- **Comorbidities:** Charlson comorbidity index
- **Cirrhosis etiology:** AH, HBV, HCV, NAFLD, cryptogenic, autoimmune, and other
- **Baseline cirrhosis substage:** compensated without varices, compensated with varices, and decompensated
- **Baseline serum labs:** total bili, AST, ALT, albumin, INR, platelets, creatinine, calculated MELD and FIB-4 scores
- **Study procedure date:** date of endoscopy and DECT
- **Procedure complications:** From DECT or endoscopy
- **2-year follow up to track liver-related events:** ascites, hepatic encephalopathy, bleeding varices, intervention for varices, TIPS, liver transplant, HCC, or death

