13.2 Statistical analysis plan

Patient and imaging characteristics will be summarized and compared using appropriate summary statistics, e.g. mean and standard deviation for continuous variables, frequency and percentage for categorical variables, and extensive exploratory data analysis and data visualizations will be utilized to assess diagnostics, identify outliers, and validate assumptions.

Receiver operating characteristic (ROC) analysis will be used in Aim 1 to estimate the accuracy of DECT for differentiating no varices from any varices and for differentiating no and small varices from large varices in Aim 1. Sensitivity, specificity, accuracy, and AUC along with their two-sided 95% CI will be presented separately. The grade of varices (0, 1, 2) on DECT will be correlated with the grade of varices on endoscopy (0, 1, 2) using weighted Kappa coefficient for categorical data (Aim 2.2).

The MIXED effect model will be used in Aim 2.1 to estimate the ICC for the inter-observer agreement for the detection of any varices and high-risk varices on dual energy CT. Reader experience and subject will be the two random effects in the model used for interobserver variability. The intraclass correlation coefficient (ICC) will be defined as the ratio between subject variance and the sum of variances for subject, reader experience and error term. ICC values will be characterized as very poor (0 to <0.20), poor (0.20 to <0.40), moderate (0.40 to <0.60), good (0.60 to <0.80), and very good (0.80 to 1.00).

Time to development of bleeding varices (or hepatic event) will be modeled in Aim 2.3 using Cox proportional hazards models with clustered sandwich estimators to account for within and between cluster correlations. Cause specific proportional subhazards analysis while accounting for competing risks (e.g. gastroesophageal banding) and adjusting for covariates will be utilized to assess the association between endoscopic findings and DECT findings and time to developing individual vs. any hepatic complications.

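### DECT follows the reference endoscopy, and the ROC analysis does not separate patients banded before the scan, so a correct DECT reading of a banded varix could count as an error

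*Combined protocol and SAP*

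**What the plan says.** **Order of the tests.** Section 6 states: "The patient will undergo the upper gastrointestinal (GI) endoscopy procedure and recovery per standard of care". The patient then receives the DECT appointment, "which may be on the same day as the endoscopy or within 2 weeks from endoscopy". An earlier phrase in section 6 could be read as either side of endoscopy, but the sequence of events and this wording put DECT second.

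**Treatment.** Section 2 says that patients with large varices, with small varices and red wale signs, or with small varices and decompensated cirrhosis "proceed to treatment such as prophylactic band ligation and beta blockers". It gives no timing. No section defers banding until after DECT.

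**Exclusion.** Section 4.2 excludes "History of bleeding gastroesophageal varices, variceal intervention or portosystemic shunt". Under section 5.1 the coordinator will "meet with the patient prior to endoscopy, answer questions, review the inclusion/exclusion criteria", so the criterion covers earlier interventions only.

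**Data.** The endoscopy findings in section 11.2 include no item for treatment given at that session. The clinical data table in section 11 lists the endoscopy and DECT dates and, under 2-year follow-up, "bleeding varices, intervention for varices, TIPS, liver transplant, HCC, or death". Sections 6 and 12 add phone interviews at 1 and 2 years, which ask about treatment of high-risk varices, and a search of the medical record.

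**Analysis.** Section 13.2 plans one ROC analysis for no varices against any, and another "for differentiating no and small varices from large varices". Banding appears there only as an example of a competing risk in the time-to-event models.

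**The concern.** The primary objective compares a DECT grade with an endoscopic grade on the premise that both describe the same varices. For a patient banded at or after the study endoscopy and before the scan, the reference grade is pre-treatment and the index grade is post-treatment. If the banded varix looks smaller on DECT, a correct reading is scored as a miss. At stake are the two primary AUROC estimates and their comparison with the hypothesised values: above 0.90 (any) and 0.95 (high-risk) in the study summary, and above 0.90 for both in section 13.1. Unless treated patients are identified, the report cannot show whether the effect was present or zero.

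**Working it through.** **The plan's own figure.** Section 13.1 states power above 95% for AUC 0.90 against 0.5, with 34 patients with varices and 16 without, one-sided 0.05. The Hanley-McNeil standard error is 0.0884 at AUC 0.5 and 0.0429 at 0.90. Then (0.40 − 1.645 × 0.0884)/0.0429 is about 5.9, so power exceeds 99.9%. The figure reproduces and is not in dispute.

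**Inputs.** The planned mix is 16 none, 16 small and 18 large (section 13.1). The high-risk contrast is 18 large against 32 none or small, giving 18 × 32 = 576 pairs. The any-varices contrast is 34 against 16, giving 544 pairs.

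**Assumptions not in the documents.** These are the number of patients banded before DECT, whether banding lowers the DECT grade within 2 weeks, and the DECT-by-endoscopy table. The illustrative table has DECT grades 0/1/2 of 15/1/0 (endoscopy none), 1/14/1 (small) and 0/1/17 (large).

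**Formula.** The AUC is the share of positive-negative pairs ranked correctly, with ties counted as one half. Let n0, n1 and n2 be the negatives graded 0, 1 and 2. A positive graded 2 scores n0 + n1 + n2/2. Graded 1, it scores n0 + n1/2. Graded 0, it scores n0/2.

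**Baseline.**
- High-risk: the negatives are 16/15/1 and the positives 0/1/17. The score is 23.5 + 17 × 31.5 = 559, and 559/576 = 0.9705.
- Any: the negatives are 15/1/0 and the positives 1/15/18. The score is 7.5 + 15 × 15.5 + 18 × 16 = 528, and 528/544 = 0.9706.

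**Moving one patient.**
- Large read as small: the high-risk loss is (n1 + n2)/2 = 8 pairs, 8/576 = 0.0139. The any-varices loss is 0.5/544 = 0.0009.
- Large read as none: 31.5 − 8 = 23.5 pairs, 23.5/576 = 0.0408 (high-risk). The any-varices loss is (16 − 7.5)/544 = 0.0156.
- Small read as none: (15.5 − 7.5)/544 = 0.0147 (any). The high-risk AUROC gains 0.5/576 = 0.0009.

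| One patient changed | High-risk AUROC | Any-varices AUROC |
|---|---|---|
| No change | 0.9705 | 0.9706 |
| Large read as small | 0.9566 | 0.9697 |
| Large read as none | 0.9297 | 0.9550 |
| Small read as none | 0.9714 | 0.9559 |

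If DECT is otherwise perfect, the loss per large varix read as small is again 8/576, because 16 of the 32 negatives are still graded 1 or 2. In that case the high-risk AUROC runs from 1.00 with no such patient to 0.75 with all 18, and a small varix read as none leaves it unchanged.

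**Scale.** On the illustrative table the Hanley-McNeil 95% half-width is 1.96 × 0.0289 = 0.057 (high-risk) and 1.96 × 0.0221 = 0.043 (any). One large varix read as small is 0.0139/0.057, about a quarter of the high-risk half-width. About four of 18 (22%) would equal it.

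**The case against.** The strongest reply is that neither necessary premise is documented. Section 2 is background and gives neither the timing of banding nor the share of patients banded. Sections 4 and 11.2 describe a surveillance procedure, and no section says that banding changes a CT grade. This stands: the size of the effect is unknown and may be zero. It does not remove the gap in the analysis plan. Beta blockers are left out of the point because no section says that they change the CT grade. For banding, the same link is an explicit assumption.

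A reader might infer a systematic loss on large varices. The documents do not support that. Two of the three treated groups in section 2 have small varices, decompensated patients are eligible, and no mix of treated patients is given. Banded small varices read as none would leave the high-risk AUROC unchanged or slightly higher.

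A reader might also infer that the study would miss its targets. On the illustrative table, two large varices read as small give 0.943, below 0.95. With otherwise perfect DECT it takes four (0.944). These crossings depend on an invented table and an unknown count, and carry no planned consequence. The only stated null is AUC 0.5, and section 13.2 presents estimates with confidence intervals in a 50-patient pilot.

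It is also fair that the data are largely collected already: follow-up counts from endoscopy, so the interval before DECT falls within it. That makes the fix cheaper. It does not supply the missing rule in the ROC analysis.

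**Conclusion.** The gap is real but conditional. As written, a patient banded before DECT enters both primary ROC analyses with a pre-treatment reference and a post-treatment index test, and neither the exclusion nor the analysis plan separates that patient. Bias follows only if banding occurs before the scan and lowers the DECT grade by then. The documents establish neither.

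The direction depends on who is banded. Large varices read as small lower the high-risk AUROC by about 1.4 points each and hardly move the any-varices AUROC. Large varices read as none lower both. Small varices read as none lower only the any-varices AUROC, by about 1.5 points each. The per-patient figures assume the planned 16/16/18 mix and the tables above.

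This is an inexpensive improvement to consider, held with low confidence as to its practical effect.

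**What to change.** Derive a treated-before-DECT flag, with the date and type of treatment, from the interventions and procedure dates already collected. The competing-risks analysis needs the banding date in any case. Report the number treated. Prespecify both primary AUROCs for all patients and, as a sensitivity analysis, without patients who had endoscopic variceal treatment before DECT.

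The cost is one derived field and one extra analysis. The untreated subset has fewer high-risk patients, a shifted spectrum and a wider interval. At AUC 0.9705 against 32 negatives, the high-risk half-width rises from 0.057 to 1.96 × 0.0405 = 0.079 if 9 of 18 large varices were treated, and to 1.96 × 0.0495 = 0.097 if 12 were. Both results should therefore be reported.

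Scanning before elective banding should be left to scheduling convenience. It cannot help with bands placed during the study endoscopy unless DECT is moved ahead of that procedure. The endoscopist would then have to be kept from the DECT report, which section 8.5 places in the medical record.

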7. RISKS

- 7.1 Breach of Confidentiality – There is an unlikely potential risk of a breach of confidentiality.
- 7.2 Intravenous (IV) Catheter Placement - Participants may experience pain, bruising or bleeding at the IV catheter site. There is a very small risk for developing an infection.
- 7.3 Contrast Injection – Patients will receive FDA-approved iodinated contrast (dye) through an IV-line during the dual energy CT scan. The contrast is essential for improving visualization of varices. There is a small risk of IV-line infiltration. Immediately following injection, patients may feel a mild warm feeling that will go away in a few seconds. Uncommon side effects include physiologic reactions and allergic-like reactions such as abnormal heart rate, nausea, dry mouth, itching, hives, cough, or shortness of breath. Very rarely, people can experience life-threatening allergic reactions to iodinated contrast. The CT contrast dye can rarely cause kidney injury in patients who already have severe kidney disease.
- 7.4 Radiation – Study participants will be exposed to radiation from the DECT imaging. There is an extremely low risk that the radiation may cause cancer or other radiation effects years after the study. Exposure to the radiation through this study is not part of routine healthcare.
- 7.5 Risk of an Unexpected Imaging Finding – There is a risk that an unexpected imaging finding could be detected. In many cases, these are of benefit to the patient, such as detection of a unexpected cancer. In some cases, the unexpected finding may be indeterminate, such as a renal mass that is not clearly benign or malignant. Indeterminate findings may need additional workup that will not be covered as a part of this study.

8. PRECAUTIONS / MINIMIZATION OF RISKS

Participants will be monitored by study personnel for risks—physical, psychological, social, economic, and/or legal—that participants may encounter during their participation in this study or as a result of DECT imaging and data collection required in this protocol.

- 8.1 Breach of Confidentiality – The research team is experienced and will utilize best practices to avoid a breach of confidentiality. The risk of confidentiality will be minimized by collecting only the data that is required by the study, labeling all data forms and samples with a coded identifier, and maintaining all study records in locked files or password-protected computer files.
- 8.2 Intravenous (IV) Catheter Placement - The radiology technologists are experienced with IV-line placement and will utilize best practices to minimize pain and avoid bruising, bleeding, and infection.
- 8.3 Contrast Injection – A power injector will be used to assist with detecting IV-line infiltration. The radiology technologists are trained to manage physiologic and allergic-like reactions, and there is a physician available for more severe reactions. Kidney function will be tested in all participants through a blood draw prior to the receiving the contrast. Patients who have had a prior allergic reaction or have severe kidney disease cannot participate in this study. All patients will be monitored for reactions during this study.
- 8.4 Radiation – The total radiation exposure is expected to be 16 mSv, equivalent to about 2.6 years of exposure to natural background radiation. Background radiation is radiation normally received from sources such as cosmic rays and natural radioactivity in building materials and the ground. Exposure to the radiation through this study is not part of routine healthcare. The

amount of radiation exposure has been minimized by the research doctors. For example, a normal liver CT for evaluation of cirrhosis includes 4 different scans of the liver, but this research scan only include 2 scans of the liver and therefore half the amount of radiation.

8.5 Risk of an Unexpected Imaging Finding – All of the research DECT liver CTs will be interpreted by a radiologist, a physician with expertise in CT imaging. A formal report will be placed permanently in the electronic medical records. Clinically significant unexpected imaging findings will be communicated by phone with the gastroenterologist, per standard of care at UAB.

